### 9.4 Qualitative Interview Guide

We will use a semi-structured interview guide to explore the following: 1) caregiver perception of the acceptability and content of the intervention; and 2) caregiver perceptions of the benefits of receiving the intervention. Facilitators will use probes to obtain a comprehensive understanding of the caregivers' perspectives. The semi-structured interview guide is detailed in Appendix R. The interview will last approximately 30 minutes. The qualitative interview will be conducted in-person or over the phone.

### 9.5 Data from the Electronic Health Record

## PROTOCOL TITLE: Proof-of-Concept Trial of a Positive Psychology Intervention for Caregivers of Patients with Hematologic Malignancies Undergoing Hematopoietic Stem Cell Transplantation

Since this is a caregiver study and caregivers are not patients, we will not be obtaining any patient information from the electronic health record.

### 9.6 Data Collection

We will collect and enter all caregiver-reported data electronically using Research Electronic Data Capture (REDCap). The REDCap Survey is a tool for building and managing online surveys. Vanderbilt University, in collaboration with a consortium of institutional partners, has developed this software and workflow methodology for electronic collection and management of research and clinical trial data. Our research team has extensive experience using REDCap and will create and design the surveys in a web browser, with institutional information technology support. The REDCap Survey system offers secure, HIPAA compliant, web-based applications that provide an intuitive interface for participants to enter data, with real-time validation rules at the time of entry.

Participants will be e-mailed a remote access link to the REDCap system [Appendix S] containing questionnaires for them to complete or they can complete questionnaires during in-person clinic visits. If any participants refuse or are unable to complete the questionnaires on the computer, they will be permitted to use hard-copy paper. Participants will also be provided the option to complete questionnaires over the phone. The CRC will contact participants (in-person or via telephone) daily for two days to remind them to complete and return the surveys. If study participants fail to complete the surveys within seven days of the expected time point, we will report the data as missing and document the reason for incompleteness. Table 4 details the schedule for administering the self-report measures.

Table 4: Administration of Self-Report Measures		
Participant	Baseline	Week-9 (+ 1 week window)
Patient Measures:		
Demographics	X	
CarGOQOL	X	X
CRA	X	X
HADS	X	X
CASE-t	X	X
MOCS	X	X
Accelerometer	X	X
LOT-R	X	X
PANAS	X	X
SWLS	X	X
GQ-6	X	X
Flourishing Scale	X	X

### 9.7 Overview of Research Procedures

Initial/Enrollment phone call: During this initial approach during the patient's HSCT hospitalization or during a routine clinic visit up to their day 100 post-transplant, or with patient permission a phone call after the consent visit, the study procedures will be explained to potential participants. Those who are interested will be screened for eligibility. Eligible participants will be enrolled and asked to complete verbal consent procedures. Consented participants will also be mailed (or given in person at a routine follow-up visit) the study intervention manual.

**PROTOCOL TITLE: Proof-of-Concept Trial of a Positive Psychology Intervention for Caregivers of Patients with Hematologic Malignancies Undergoing Hematopoietic Stem Cell Transplantation**

**Baseline Assessments:** At enrollment all participants will be mailed the Actigraph GT3X+ with instructions on how to use the Actigraph for 7 days of wear; minimum acceptable use is 4+ days with 10+ hours of recorded data prior to the intervention initiation. After baseline physical activity data collection, participants will mail back the Actigraph in prepaid envelopes we will provide. Within a week of consenting to participate in the study, participants will be asked to complete baseline assessment questionnaires either in-person during a routine follow-up visit in clinic, over phone, or via a REDCap survey link that will be e-mailed to participants before intervention initiation.

After completion of the baseline survey, the interventionist will review the mailed treatment manual with weekly PP exercises. Participants will be assigned the first exercise (gratitude for positive events) in preparation for their first phone session.

**Weekly phone sessions for positive psychology intervention:** All participants will be asked to complete the 9 weekly PP exercises and to speak with the interventionist weekly. Weekly phone sessions will last approximately 15-20 minutes. Prior to completing each phone session, participants will be asked to rate their current level of happiness and optimism, using a 10-point Likert scale. Immediately after completing the exercise and phone session, participants will rate the ease of exercise/session completion, overall utility of the exercise/phone session, and their current levels of happiness and optimism, all using 10-point Likert scales. These calls will be recorded so that a percentage (10%) of these recordings can be reviewed by [name], to ensure that the PP intervention is being delivered as described in the protocol. Given the results of our prior PP studies in medical populations yielding a 64-85% completion rate of the exercises, our recent proof-of-concept trial (18-225) yielding 100% completion rate among HSCT recipients, and that this is a feasibility study (i.e., we want to assess participants' willingness to complete the phone sessions), we will expect participants to complete at least 6 PP exercises. In other words, if a participant completes at least 6 sessions, missed sessions will not be considered a deviation from the protocol.

**Follow-up assessments:** At Week 9, participants will repeat self-assessment questionnaires obtained at the beginning of the study either in-person, during a routine follow-up clinic visit, over the phone, or via a REDCap survey link e-mailed to them, depending on participant's preference. A week prior to intervention completion, participants will be mailed the Actigraph GT3X+ for follow-up physical activity data collection and participants will mail back the Actigraph in prepaid envelopes we will provide. Furthermore, participants will be asked to provide feedback about the program via a recorded exit interview over the phone.

**Positive Psychology Program Content:** All phone sessions will include (a) a review of the ease and utility of the week's PP exercise, (b) a discussion of the rationale of the next week's PP exercise through a guided review of the PP manual, and (c) assignment of the next week's PP exercise. During the calls, the interventionist and participant will also review the next section of the treatment manual and prepare for the upcoming week's exercise.

#### *9.8 Procedures performed to lesson the probability or magnitude of risks*

We will ensure that contact with participants is confidential by using only the phone numbers and other contact information that are specifically allowed by the participants. We will not leave study-related messages for participants unless expressly allowed by participants. Upon enrollment, we will ask all participants for the

**PROTOCOL TITLE: Proof-of-Concept Trial of a Positive Psychology Intervention for Caregivers of Patients with Hematologic Malignancies Undergoing Hematopoietic Stem Cell Transplantation**

preferred times for calls and if it is acceptable to leave voice messages on their phones. We will adhere to any and all patient requests regarding contact.

Digital recordings of the sessions and exit interviews will be completed using portable recorders. If a study participant were to refuse audio recordings, they can work with the study staff to choose an alternative to audio recording such as transcription. All recordings will be downloaded immediately from the recorders and the electronic files will be kept within the firewalled, password-protected file on a Partners/Mass General Brigham/DFCI server. Recordings will contain no personally identifiable information (names or other identifying information on the recordings will not be used) and will be erased following review.

## **10.0 Data and Specimen Banking: Not Applicable**

### *10.1. Data analysis*

We will use descriptive statistics (e.g., mean) for continuous variables and proportions for categorical variables to summarize the demographic and clinical characteristics of caregivers enrolled in the study.

**Specific Aim 1 (Phase 1: Intervention Refinement): To refine a positive psychology intervention, PATH, in caregivers of HSCT recipients based on findings from an open-pilot study.** Informed by our prior work, our planned sample size (N=5) will allow us to obtain comprehensive feedback about the intervention for refinement. The qualitative exit interviews will explore the following themes: 1) caregiver perception of intervention content; 2) barriers/challenges with the delivery method; and 3) modifications to promote caregiver engagement. All exit interviews will be recorded, transcribed, coded, and thematically analyzed using a directed content analysis. Findings from phase-1 will be used to refine and finalize the intervention for feasibility testing in phase 2. Participant feedback of the study assessments/questionnaires will also help to refine the study procedures for the phase-2 of this project.

**Specific Aim 2 (Feasibility and Acceptability): To assess the feasibility and acceptability of the PATH intervention for caregivers of patients undergoing HSCT.** Based on prior work, we define feasibility as >60% of eligible participants enrolling for the study and >60% of enrolled participants who start the intervention completing at least 6 of the 9 PP sessions, consistent with metrics used in prior positive psychology feasibility trials and other behavioral intervention studies. We will estimate the feasibility using the proportion who meet the criteria, and we will place an exact 95% binomial confidence interval around the proportion. We will assess acceptability using weekly ratings of ease and utility of each exercise (0=very difficult/not helpful; 10=very easy/very helpful). The mean ease and utility of each exercise will be calculated, and we will use a threshold mean combined score of 7.0/10 for acceptability that was used in prior studies.

**Qualitative Data Analysis:** For all exit interviews, two research staff will independently review the transcripts to create a thematic framework for interpretation. Dedoose 8.0.35 software (SocioCultural Research Consultants, LLC: Los Angeles, CA) will be used for data organization and management. We will code and analyze the data using directed content analysis, a descriptive approach to qualitative analysis. Codes will be informed by the interview guide and qualitative interview data, and the framework for the coding tree will be informed by conceptual models per existing qualitative methods. Overall with qualitative data, we will explore intervention acceptability, proposed intervention content (e.g., PP exercises), and delivery preferences (e.g., intervention duration, call frequency).

**PROTOCOL TITLE: Proof-of-Concept Trial of a Positive Psychology Intervention for Caregivers of Patients with Hematologic Malignancies Undergoing Hematopoietic Stem Cell Transplantation**

*10.2 Sample Size Calculation & Power Analysis:*

Given that this pilot is a one-arm feasibility study, we will not be able to estimate sample sizes or complete a power analysis. Although we will be administering patient reported outcomes for phase 2, the primary reason is feasibility of study procedures and we are not powered to detect statistically significant group differences.

*10.3 Data security*

Participant data will be collected using REDCap. We will maintain a separate list of participant names and study IDs, which will be saved in password-protected files. Participants will be identified on study forms by case number only to protect confidentiality. Identifiers such as names will only be used during the initial data retrieval process and can be destroyed once all data records have been obtained and data analysis has been completed as discussed previously.

Participants' responses to survey questions will remain confidential unless there is active suicidal ideation confirmed by the research team. Under these circumstances, as clearly stated in the participant consent form, the study CRC will inform the PI who will determine the need to involve social work, psychiatry and/or take further action as deemed necessary.

We will ensure that contact with participants is confidential by using only the phone numbers and other contact information that are specifically allowed by the participants and not leaving study-related messages for participants unless expressly allowed by participants. Upon enrollment, we ask all participants if it is acceptable to leave voice messages on their phones, as well as the appropriate times to call them. We will adhere to all participant requests regarding contact.

In addition, as stated previously, all study staff will undergo an extensive training on study procedures as well as data management to ensure data security and maintaining of confidentiality.

*10.4 Quality control for collected data:*

Our study staff will utilize double-data entry for approximately 10% of the data entered through REDCap to ensure high data quality. A CRC, blinded to the study intervention, will double enter 10% of the data through REDCap to check on data fidelity. If an error is found, the research coordinator will double enter an additional 5% of the data through REDCap. This process will continue until no errors are found. Also, the CRC will perform 'test downloads' of the data to ensure that it can be captured in the statistical package to be used in this study.

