**1.2 Specific Aims/Objectives and Hypothesis**

**Specific Aim 1 (Phase 1: Intervention Refinement):** To refine a positive psychology intervention (PATH) in caregivers of HSCT recipients based on findings from an open-pilot study (N=5).

**Specific Aim 2 (Phase 2: Feasibility):** To determine the feasibility and acceptability of the refined PATH intervention and our assessment battery in caregivers of patients who have undergone HSCT using a single-arm trial (N=20).

*Hypothesis 1:* *The intervention will be deemed feasible if >60% of eligible participants enroll and >60% of enrolled participants complete ≥6/9 positive psychology (PP) exercises.*

*Hypothesis 2:* *The intervention will be deemed acceptable if weekly ratings of ease and utility of the PP exercises are >7/10 on a 10-point Likert Scale (0=very difficult/not helpful; 10=very easy/very helpful).*

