
Phase-1: Caregivers who provide informed consent will then be registered with ODQ and scheduled for their first study intervention visit via telephone. Caregivers who withdraw from the study during the study period will not be replaced and they will count towards the accrual numbers.

Phase-2: Enrolled caregivers will complete baseline self-assessment questionnaires [Appendix C] within a week window from study enrollment. Caregivers who provide informed consent and complete the baseline questionnaires will then be registered with ODQ and scheduled for their first study intervention visit via telephone. If a caregiver signs the consent form but does not complete the baseline questionnaires, they will be

**PROTOCOL TITLE: Proof-of-Concept Trial of a Positive Psychology Intervention for Caregivers of Patients with Hematologic Malignancies Undergoing Hematopoietic Stem Cell Transplantation**

excluded from the study. Caregivers who withdraw from the study during the study period will not be replaced and they will count towards the accrual numbers.

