## PROTOCOL TITLE: Proof-of-Concept Trial of a Positive Psychology Intervention for Caregivers of Patients with Hematologic Malignancies Undergoing Hematopoietic Stem Cell Transplantation

from the Covered Entity by the researcher; and 3) the Protected Health Information for which we are requesting access is necessary for research purposes.

Participants will be registered with the Clinical Trials Management System after they have verbally consented and completed baseline assessments. Participants who withdraw from the study or die during the study period will not be replaced and they will count towards accrual numbers.

DF/HCC institutions will register eligible participants in the Clinical Trials Management System (CTMS) Oncore as required by DF/HCC SOP REGIST-101. Registration must occur after the initiation of protocol-specific procedures or assessments.

For registration of participants from the DF/HCC institutions, study staff will complete the DF/HCC protocol-specific eligibility checklist. Study staff will confirm that the participant meets all inclusion criteria as described in this protocol. Study staff will then register study participants through OnCore. Study staff will follow DF/HCC Standard Operating Procedure for Human Subject Research Titled *Subject Protocol Registration* (SOP #: REGIST-101) and register the participant on the protocol.

Once the caregiver has been enrolled, they will be asked to complete baseline study measures. Registration Process for DF/HCC Institutions DF/HCC Standard Operation Procedure for Human Subject Research Titled Subject Protocol Registration (SOP#: REGIST-101) must be followed. For each study participants, we will complete the following registration procedures:

- We will obtain written informed consent from the participant prior to the performance of any protocol specific procedures or assessments.
- We will complete the ODQ protocol-specific eligibility checklist using the eligibility assessment documented in the participant's medical record and/or research chart. Only eligible participants will be registered. To be eligible for registration to the protocol, the participant must meet all inclusion and exclusion criteria as described in this protocol and reflected on our eligibility checklist.
- We will fax the eligibility checklist(s) and all pages of the consent form(s) to the ODQ at [contact].
- The ODQ Registrar will (a) review the eligibility checklist and (b) register the participant on the protocol.

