## **8.0 Study Endpoints\***

*Primary Endpoint:*

- Establish the feasibility and acceptability of the PATH intervention and completing the assessment battery in 20 caregivers of HSCT recipients.

*Secondary Endpoints:*

- Establish the feasibility of study procedures (e.g., use of assessment measures like actigraphy for physical activity) in caregivers of HSCT recipients in preparation for larger preliminary efficacy trial.
- Determine the proportion of caregivers completing intervention visits
- Establish the duration of the intervention visit
- Determine the proportion of caregivers completing study assessments

*Primary or secondary safety endpoints:*

- None

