### 9.2 *The PATH Intervention*

After the initial phone visit to introduce the concept of positive psychology and the PATH intervention, participants will be asked to complete 9 weekly positive psychology exercises with the study interventionist over the phone.

**Table 2. PP intervention component:** modules and exercises. Intervention content will be customized to HSCT context.

Module 1: Gratitude/positive affect-based exercises		
Week 1	Gratitude for positive events 	Participants identify three positive events that have occurred in the past week and reflect on their feelings as they recall and describe these events.
2	Gratitude letter 	Participants write a letter of gratitude thanking a person for their support or kindness.
3	Gratitude skills application	Participants select a useful activity from the prior two weeks, consider how to adapt the activity to daily life, and develop a plan to utilize this skill regularly.
Module 2: Strengths-based exercises		
Week 4	Recalling past success 	Participants recall an event in which they experienced success, then write about the event, their contribution to the success, and positive feelings elicited by recalling it.
5	Using personal strengths 	Participants undergo a brief assessment of personal strengths, then find a specific new way to use one of their 'signature strengths' in the next 7 days.
6	Strength-based skills application	Participants select a useful activity from the prior two weeks, consider how to adapt the activity to daily life, and develop a plan to utilize this skill regularly.
Module 3: Optimism and meaning-based exercises		
Week 7	Enjoyable and meaningful activities 	Participants complete three activities: an enjoyable activity alone, an enjoyable activity with another person, and a meaningful activity completed alone or with others.
8	The good life 	Participants imagine and write in detail about a best possible (realistic) future one year from now and consider small short-term steps to take toward such a future.
9	Skills application + future planning	Participants select an activity from this module and develop a plan to utilize this skill—and additional skills from the program—this week and beyond

As shown in Table 2 above, the PATH intervention will focus on three main modules: 1) gratitude/positive affect-based exercises; 2) strengths-based exercises; and 3) optimism and meaning-based exercises.

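### The completion criterion for feasibility has two denominators, all enrolled caregivers (1.2) and only those who start (10.1), and near 60% the two can give opposite verdicts

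*Combined protocol and SAP*

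**What the plan says.** Section 8.0 makes feasibility part of the primary endpoint: "Establish the feasibility and acceptability of the PATH intervention", to be assessed in 20 caregivers. Two proportions decide feasibility: enrolment among those eligible, and completion of at least 6 of the 9 weekly units. This point concerns the second.

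- Section 1.2, Hypothesis 1, deems the intervention feasible if ">60% of enrolled participants complete ≥6/9 positive psychology (PP) exercises". The denominator is everyone enrolled and the unit is the exercise.
- Section 10.1, Specific Aim 2, defines the criterion as ">60% of enrolled participants who start the intervention completing at least 6 of the 9 PP sessions". The denominator is enrolled caregivers who start and the unit is the session. The same paragraph plans an exact 95% binomial interval around the proportion.

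On who is among the 20, section 3.1 says of phase 2: "Caregivers who provide informed consent and complete the baseline questionnaires will then be registered with ODQ and scheduled for their first study intervention visit". It adds: "Caregivers who withdraw from the study during the study period will not be replaced and they will count towards the accrual numbers". Section 5.1 repeats this: "Participants who withdraw from the study or die during the study period will not be replaced and they will count towards accrual numbers". Sections 3.1 and 21.0 leave out phase-2 caregivers who consent but skip the baseline questionnaires, so they are not at issue here.

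**The concern.** Both statements are current, both are worded as decision rules, and neither refers to the other. Registration comes before the first intervention visit. A caregiver who withdraws in between is one of the 20 and is not replaced, but has started nothing. Section 1.2 counts that caregiver as a failure; section 10.1 removes them.

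The event that marks a start is also open. It could be the introductory call in section 9.2 ("After the initial phone visit to introduce the concept of positive psychology and the PATH intervention"), the assignment in section 9.7 ("Participants will be assigned the first exercise (gratitude for positive events) in preparation for their first phone session"), or the first weekly session itself. Each choice gives a different starters-only denominator.

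Dropping people on something that happens after enrolment can only raise the completion rate for a given number of completers. With no rule fixed beforehand, the denominator could be settled once the counts are known, and the looser choice always favours a feasible verdict. The study is meant to prepare larger efficacy trials, and the timeline in section 7.0 includes a grant proposal for one, so the reported verdict matters.

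**Working it through.** The plan gives no power calculation or expected completion figure for this criterion (section 10.2), so there is no stated result to reproduce. The check applies the two rules to the same counts.

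**Inputs.** Enrolled N = 20 (sections 4.0 and 8.0); threshold strictly above 60% (1.2 and 10.1); S = number who start; C = number who complete at least 6 of 9. The documents give no non-start rate, so it is assumed below.

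**Step 1: the rules.**
- Section 1.2: C/20 > 0.60, so C ≥ 13, because 12/20 is exactly 60.0%.
- Section 10.1: C/S > 0.60.

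**Step 2: where the verdicts differ**, with exact (Clopper-Pearson) 95% intervals.

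| Start | Complete | Of enrolled (1.2) | Of starters (10.1) |
|---|---|---|---|
| 20 | any | same | same |
| 19 | 12 | 60.0% (36.1–80.9), fails | 63.2% (38.4–83.7), passes |
| 18 | 11 | 55.0% (31.5–76.9), fails | 61.1% (35.7–82.7), passes |
| 18 | 12 | 60.0% (36.1–80.9), fails | 66.7% (41.0–86.7), passes |

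With 17 starters the verdicts differ at 11 or 12 completers, and with 16 starters at 10, 11 or 12. Since S ≤ 20, C/S is never below C/20, so the disagreement runs one way only.

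Every interval in the table includes 60%, and the plan attaches no rule to an interval bound. The verdict therefore rests on the point estimate and its denominator.

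**Step 3: chance of a flip given the number of non-starters.** Let p be the share of starters who complete. With one non-starter the chance is P(C = 12) for C ~ Binomial(19, p). With two it is P(C = 11 or 12) for C ~ Binomial(18, p).

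| p | One non-starter | Two non-starters |
|---|---|---|
| 64% | 18.6% | 37.5% |
| 70% | 15.3% | 32.5% |
| 75% | 9.7% | 22.6% |
| 85% | 1.2% | 3.9% |
| 100% | 0% | 0% |

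**Step 4: overall chance of opposite verdicts.** Take S ~ Binomial(20, 1 − non-start rate) and C given S ~ Binomial(S, p), and sum over all pairs (S, C) where the rules differ.

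| p | 2% do not start | 5% | 10% |
|---|---|---|---|
| 64% | 7.3% | 17.2% | 29.9% |
| 70% | 6.2% | 15.1% | 28.7% |
| 75% | 4.1% | 10.7% | 22.6% |
| 85% | 0.6% | 2.1% | 7.0% |
| 100% | 0% | 0.0% | 0.04% |

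The values of p from 64% to 100% span the completion figures that section 9.7 quotes from earlier work. The 64–85% there is a completion rate for exercises, not the share of people reaching 6 of 9, so the grid is illustrative.

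**The case against.** The strongest reply is that section 10.1 is the analysis section. It says how feasibility is defined and then gives the estimator and interval, so it can be read as making the one-line hypothesis in 1.2 more specific. That may be the intent. But Hypothesis 1 is itself a decision rule, and section 10.1 neither replaces it nor says how enrolled non-starters are counted. Even if 10.1 governs, 1.2 has to be aligned and a start defined.

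A second reply is that non-starters will be rare. Registration already requires a completed baseline, section 11.0 calls refusal after enrolment in the previous trial quite low, and section 9.7 reports 100% completion in the earlier patient trial. This limits the size: at 2% non-start the disagreement is at most 7.3% in the grid above, and at 100% completion it is essentially nil. But quite low is not zero, and the statement in 11.0 that all completed is conditional on having started, so it gives no non-start rate.

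Third, no progression or stopping rule depends on the verdict, and 12/20 and 12/19 have nearly the same interval. That is right, and it confines the harm to the reported conclusion. Starters-only completion is also a legitimate measure; the fault is in not choosing.

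Two side issues carry little weight. Exercises and sessions are named as different units, but section 9.7 largely equates them. Section 12.0 leaves open whether a withdrawn caregiver's data are analysed, but a caregiver who starts and then withdraws early stays in both stated denominators.

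**Conclusion.** The concern holds. Sections 1.2 and 10.1 set conflicting thresholds for one of the two proportions that decide the primary endpoint, and nothing in the plan ranks them. One non-starter is enough for opposite verdicts, at exactly 12 completers; two widen this to 11 or 12. If all 20 start, the conflict disappears. The integer flip points need no assumption beyond N = 20. The probabilities do: under assumed non-start rates of 2% to 10% they run from about 30% (64% of starters complete, 10% do not start) to practically zero when all starters complete. The conflict should be resolved before results are seen, although no stop or progression decision hangs on it.

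**What to change.** State one rule, in the same words, in sections 1.2 and 10.1 before results are seen. Suggested text: *the completion criterion is met if more than 60% of all registered phase-2 caregivers (consented, baseline completed) complete at least 6 of the 9 PP exercises; caregivers who never start, withdraw or are lost count as not completing.* This keeps the denominator of Hypothesis 1 and fits the accrual rules in 3.1 and 5.1.

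- Put the exact 95% interval on that proportion.
- Report the starters-only rate as a labelled secondary result, with a start defined as one event, for example taking part in the first weekly phone session.
- Use one completion unit, exercise or session, in both sections.
- Say in section 12.0 that withdrawn caregivers stay in this denominator.

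If the investigators prefer starters-only as the primary rule, naming it in both sections, defining a start and reporting the all-registered rate beside it would also remove the contradiction. The all-registered rule is the safer choice because it cannot be raised by exclusions after enrolment.

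The cost is a few sentences in three sections and no extra data or participants. The reported rate may be lower than under the starters-only rule.
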